2.4.4.2 Analyses of key secondary efficacy endpoints

2.4.4.2.1 Analysis of the change from baseline in LMK, TSS, UPSIT score, the daily loss of smell assessment, and SNOT-22 scores at Week 24 for dupilumab 300 mg q2w versus placebo

The change from baseline in LMK TSS, SNOT-22, UPSIT score, daily loss of smell at Week 24 will be assessed for dupilumab 300 mg q2w (pooled A and B arms) versus placebo and will be analyzed using the hybrid method of the WOCF and the MI the same as the primary approach of the co-primary endpoints. Descriptive statistics including number of patients, mean, standard error, and least squares (LS) means will be provided. In addition, difference in LS means and the corresponding 95% confidence intervals (CI) will be provided along with the p-values.

Note: LMK will not be a secondary endpoint for Japan as it is already a co-primary endpoint.

2.4.4.2.2 Analysis of the change from baseline in NPS, NC and SNOT-22 at Week 52

The change from baseline in NPS, NC and SNOT-22 at Week 52 will be assessed respectively for dupilumab 300 mg q2w (Arm A) and dupilumab 300 mg q2w/q4w (Arm B) versus placebo (Arm C) (Note treatment has three levels: Arm A, B and C) and will be analyzed using the hybrid method of the WOCF and the MI in the same way as the primary analysis approach for NC and NPS except at Week 52 instead of Week 24.

Descriptive statistics including number of patients, mean, standard error, and least squares (LS) means will be provided. In addition, difference in LS means and the corresponding 95% confidence intervals (CI) will be provided along with the p-values.

2.4.4.2.3 Analysis of proportion and time-to-event of patients requiring rescue treatment defined as: use systemic corticosteroids or NP surgery (actual or planned) during the treatment period for dupilumab 300 mg q2w versus placebo

Proportion of patients requiring rescue treatment defined as: use SCS or NP surgery (actual or planned) during the treatment period will be derived and analyzed using the Cox proportional hazards model. The event of interest is the first SCS use or NP surgery (actual or planned), whichever is earlier if both occur. The decision date of surgery for nasal polyps or the first SCS intake date will be used as the event date, whichever is earlier if both occur. In case the decision date of NP surgery is missing, the planned surgery date will be used in place. In case the planned surgery date is also missing, the actual surgery date will be used in place.

Due to potential low number of events in each single study, proportion of patients requiring rescue treatment defined as: use SCS or NP surgery (actual or planned) during the treatment period for dupilumab 300 mg q2w versus placebo will also be analyzed by pooling the two NP studies SINUS-52 (EFC14280, the study this SAP is for) and SINUS-24 (EFC14146). In the pooled analysis, the treatment period by dupilumab 300 mg q2w will be the total of the entire treatment period in Arm A of EFC14280, the treatment period of 300 mg q2w in Arm B (that is, the first 24 weeks) of EFC14280, and the entire treatment period in Arm A of EFC14146; and the treatment period by placebo will be the total of the entire treatment period in Arm C of EFC14280 and the entire treatment period in Arm B of EFC14146.

The pooled data will be analyzed by the Cox model. The Cox model will include the event as the dependent variable, and a study indicator (0 for EFC14280 and 1 for EFC14146), treatment group, asthma/NERD strata, prior surgery strata, and region (pooled countries) as covariates. Hazard ratio and corresponding 95% CI and p values will be estimated for dupilumab 300 mg q2w versus placebo. The Kaplan-Meier method will be used to derive the probabilities that a patient would experience events up to Week 52 for 300 mg q2w and placebo. Kaplan-Meier curves will be generated; quartiles and point probabilities will be calculated. Interval estimates will be calculated using 95% point wise confidence intervals.

2.4.4.2.4 Analysis of the change from baseline in FEV1 at Week 24 for asthma patients

The change from baseline in FEV1(L) at Week 24 will be assessed by pooling the two NP studies SINUS-52 (EFC14280, the study this SAP is for) and SINUS-24 (EFC14146). The missing data in FEV1 at Week 24 will be imputed using the hybrid method of the WOCF and the MI the same as the primary approach of the co-primary endpoints. Each of the imputed complete data will be analyzed by fitting an ANCOVA model with the change from baseline in FEV1 at Week 24 as the response variable, and a study indicator (0 for EFC14280 and 1 for EFC14146), the baseline value of FEV1, treatment group, prior surgery strata, and region (pooled countries) as covariates. Statistical inference obtained from all imputed data will be combined using Rubin's rule. Descriptive statistics including number of patients, mean, standard error, and least squares (LS) means will be provided. In addition, difference in LS means and the corresponding 95% confidence intervals (CI) will be provided along with the p-values.

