During the study patients who report deterioration requiring medical/surgical intervention may come to the site for an endoscopy and clinical evaluation. An unscheduled visit may be used for this purpose and if necessary the Investigator may consider one of the treatment alternatives described in [Section 8.2.2](#). If surgery is scheduled after the planned end of study, EOS visit will not be delayed. A follow up contact(s) should be performed around the time of planned surgery to document the surgery date and outcome (see [Section 9.2.1.5](#)). Surgery data will be collected until e-CRF closure of the trial.

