### Surgery (actual or planned) for NP

For patients who undergo or are planned for sino-nasal surgery for NP, the reason (worsening signs and/or symptoms during the study), the expected and real surgery date, the type and outcome of surgery will be recorded in a specific CRF page. If surgery

- Is performed during the study treatment period, patient and Investigator may decide to continue IMP up to the time of surgery or EOT whichever date comes first. At the time of surgery patients will be permanently discontinued from study treatment and assessed as soon as possible using the procedures normally planned for the EOT Visit and will be instructed to return to the study site as described in [Section 10.3.1](#). An AE or serious adverse event (SAE) page will be completed.
- Is performed during the follow-up the patients will be assessed according to the procedures normally planned for the EOS Visit and will be instructed to return to the study site as described in [Section 10.1.15](#). An AE or SAE page will be completed.
- If surgery is scheduled after the planned end of study, EOS visit will not be delayed. A follow up contact(s) should be performed around the time of planned surgery to document the surgery date and outcome. Surgery data will be collected until e-CRF closure of the trial.

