information (daily dose, duration, INN) on the appropriate page(s) of the e-CRF. Indication for SCS use is captured by selecting one or more of the following categories:

1. Nasal polyposis.
2. Asthma.
3. Other respiratory disease (specify).
4. Other ear, nose or throat disease (specify).
5. Other reason (specify).

Surgery (actual or planned) for NP

For patients who undergo or are planned for sino-nasal surgery for NP, the reason (worsening signs and/or symptoms during the study), the date of decision for surgery, the planned date and the effective surgery date, the type and outcome of surgery is recorded in a specific e-CRF page. If surgery:

- Is performed during the study treatment period, patient and investigator may decide to continue IMP up to the time of surgery or EOT whichever date comes first. At the time of surgery patients will be permanently discontinued from study treatment and assessed as soon as possible using the procedures normally planned for the EOT Visit and will be instructed to return to the study site as described in protocol. An AE or serious adverse event (SAE) page will be completed.
- Is performed during the follow-up, the patients will be assessed according to the procedures normally planned for the EOS Visit and will be instructed to return to the study site as described in protocol. An AE or SAE page will be completed.
- If surgery date is scheduled after the planned end of study, EOS visit will not be delayed. A follow up contact(s) should be performed around the time of planned surgery to document the surgery date and outcome. Surgery data will be collected until e-CRF closure of the trial.

2.1.3.2.1.7 Spirometry

Spirometry is performed at local level (study site or another facility) in the morning after withholding the last dose of salbutamol/albuterol or levosalbutamol/levalbuterol for at least 6 hours. Forced expiratory volume in one second (FEV1), forced vital capacity (FVC) and forced expiratory flow at 25% to 75% of forced vital capacity (FEF 25-75) were determined at the designated treatment visits.(9). The results of FEV1 (score in L, % of predicted normal,), FVC and FEF 25-75 were recorded in the e-CRF anytime during run-in period (before V2) for all patients and in patients with asthma for the other scheduled visits during the randomized treatment period.

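### When the surgery decision date is missing, the SAP dates the rescue event at the planned operation, which can fall outside the treatment window, so surgery planned on treatment may be dated too late or not counted

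*SAP*

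**What the plan says.** **Event and window.** The endpoint sentence in SAP 2.4.4.2.3 reads in part: "use SCS or NP surgery (actual or planned) during the treatment period will be derived and analyzed using the Cox proportional hazards model". Kaplan-Meier is used to "derive the probabilities that a patient would experience events up to Week 52". In the analysis pooled with EFC14146, Arm B contributes only its first 24 weeks. Protocol 11.4.2.2.2 likewise censors Arm B when its q2w dosing ends.

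**Event date.** "The decision date of surgery for nasal polyps or the first SCS intake date will be used as the event date", and the earlier of the two counts. Two fallbacks follow: "In case the decision date of NP surgery is missing, the planned surgery date will be used in place", and then "In case the planned surgery date is also missing, the actual surgery date will be used in place". The section sets no upper limit on a substituted date. It does not say what status a patient has if that date lies outside the window, and it plans no sensitivity analysis for the case.

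**Dates collected.** SAP 2.1.3.2.1.6 lists "the date of decision for surgery, the planned date and the effective surgery date". The protocol's list is shorter. Section 9.2.1.5 says "the expected and real surgery date, the type and outcome of surgery will be recorded in a specific CRF page", footnote i of the flow chart names the actual or planned date, and the visit sections from Week 2 onward name only the planned date. The protocol nowhere asks sites for a decision date.

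**Late operations.** Protocol 6.1 says "If surgery is scheduled after the planned end of study, EOS visit will not be delayed", and SAP 2.1.3.2.1.6 makes the same provision. Both documents also allow IMP to continue until surgery or end of treatment, so a plan made on treatment for an operation after treatment is a foreseen pathway.

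**The concern.** The main rule dates the moment when surgery was judged necessary. The fallback dates the operation itself, which cannot come before the decision and may come months later. If the operation is booked beyond the patient's window, an event that met the definition on treatment may no longer fall inside it.

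The endpoint sits in the confirmatory hierarchy (SAP 2.4.4.3), and the pooled FEV1 test can be reached only through it. The SAP itself gives the potentially low number of events per study as its reason for pooling. SAP 2.4.4.5.2 applies the same method to surgery alone, where no SCS course can keep the patient in the event count.

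**Working it through.** **1. Follow the rule for single patients** (hypothetical, with no SCS use in the window).

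| | Arm A or C | Arm B (q2w analysis) |
|---|---|---|
| Surgery decided | Week 44 | Week 20 |
| Decision date in e-CRF | missing | missing |
| Operation planned | Week 70 | Week 28 |
| Date under the fallback | Week 70 | Week 28 |
| Window closes | Week 52 | Week 24 |

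Week 70 is also after the Week 64 end-of-study visit. In both cases surgery was planned inside the window, yet the assigned date lies outside it.

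**2. Reproduce the plan's figure.** Protocol 11.1 assumes 15% (placebo, n = 120) against 5% (q2w pool, n = 240), hazard ratio 0.316, two-sided alpha 0.05, and states 87% power.

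- Hazard ratio: ln(0.95)/ln(0.85) = 0.316.
- Expected events: 120 × 0.15 + 240 × 0.05 = 18 + 12 = 30.
- Two-proportion formula, pooled variance under the null: SE0 = √(0.0833 × 0.9167 × (1/120 + 1/240)) = 0.0309. SE1 = √(0.15 × 0.85/120 + 0.05 × 0.95/240) = 0.0355. Power = Φ((0.10 − 1.96 × 0.0309)/0.0355) = 86.7%. The 87% reproduces, without dropout.
- Schoenfeld: Φ(|ln 0.316| × √(30 × 1/3 × 2/3) − 1.96) = 84.5%.

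**3. How many events could move.** The documents give no rate of missing decision dates. Assume that one third of the 30 events are surgery decisions (10) and that half of those operations are booked beyond the window.

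- All decision dates missing: 10 × 1 × 1/2 = 5 events lost, 25 left, Schoenfeld power 77.5%.
- One fifth missing: 10 × 1/5 × 1/2 = 1 event lost, 29 left, Schoenfeld power 83.3%.

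Both lines hold the hazard ratio at 0.316.

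**4. Direction of bias.** Remove 10% of events by arm and recompute the hazard ratio from the proportions:

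| Events lost | Placebo, q2w | Hazard ratio | Two-proportion power |
|---|---|---|---|
| none | 15%, 5% | 0.316 | 86.7% |
| 10% in both arms | 13.5%, 4.5% | ln(0.955)/ln(0.865) = 0.317 | 82.9% |
| 10% in placebo only | 13.5%, 5% | ln(0.95)/ln(0.865) = 0.354 | 77.7% |
| 10% in q2w only | 15%, 4.5% | ln(0.955)/ln(0.85) = 0.283 | 90.2% |

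Even loss costs power and leaves the ratio almost unchanged. Uneven loss can move it either way.

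**The case against.** **The date is collected.** SAP 2.1.3.2.1.6 places the decision date on a specific e-CRF page, so the fallback may rarely be needed. This stands as a limit on size. It does not remove the point, because the protocol never requests that date and the SAP itself provides for its absence.

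**Censoring is not stated.** A reader might infer that such a patient is certainly analysed as rescue-free. The documents do not say so. On a fair alternative reading, surgery planned on treatment is an event by definition and the fallback only supplies its time. That objection stands: censoring is an inference from the treatment-period limit and the Week 52 horizon. Even on the milder reading the event is dated too late, and the patient in the first example is event-free through Week 52.

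**Other events protect the count.** SCS use for any reason inside the window keeps the patient as an event. This narrows the problem to patients with a missing decision date, a late planned date and no SCS in the window.

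**Bias toward 1.** It is tempting to say that the hazard ratio is pulled toward 1 because placebo should have more surgery. The documents do not support that. Even loss leaves the ratio near 0.32, and Arm B's 24-week window could push dupilumab events out first, which would favour dupilumab.

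**The power figures belong to another analysis.** The protocol's rates refer to this study alone and to SCS for nasal polyps. The hierarchy tests data pooled with EFC14146, with SCS for any reason, and the SAP gives no power for that. The fall to 77.5% also needs every decision date to be missing. It is an upper illustration, not an expected loss.

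**Conclusion.** The point holds as a defect in a stated rule. When the decision date is missing, the fallback dates the need for surgery at the operation. It can thereby place surgery planned on treatment outside the patient's window, contrary to an endpoint that includes planned surgery. The consequence is loss of events and power, with bias of unpredictable direction.

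The size is unknown. With one third of events being surgery decisions and half of the operations booked beyond the window, between about 1 event (one fifth of decision dates missing) and 5 events (all missing) of about 30 would be affected. These shares are assumptions, and the 30 events come from the protocol's single-study planning rates. The documents support neither a fixed direction of bias nor certain censoring.

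**What to change.** In SAP 2.4.4.2.3:

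- Count as an event any nasal polyp surgery recorded as planned within the patient's own treatment window.
- If the decision date is missing, use the earliest of the date on which the plan was first recorded in the e-CRF, the planned date and the actual surgery date.
- State the window for Arm B in the q2w analysis, and the censoring rule.
- Report the number of missing decision dates by arm.
- Apply the same rule to EFC14146 in the pooled analysis.

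A CRF completion note should ask sites to record the decision date that SAP 2.1.3.2.1.6 already lists.

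The cost is a few SAP sentences, the note, and agreement with the EFC14146 plan. The drawback is lag. After Week 24 the next scheduled visits are Weeks 40 and 52, so without an optional or unscheduled visit the recording date may trail the decision by up to about 16 weeks (40 − 24). Because the earliest of the three dates is used, the result can never be later than the date that the current fallback gives.

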#### *11.4.2.2.2 Analysis of proportion of patients with SCS rescue or surgery (actual or planned) for NP during the treatment period for dupilumab 300 mg q2w versus placebo*

Proportion of patients with first SCS rescue and/or surgery (actual or planned) for NP during the treatment period will be derived and analyzed using the Cox proportional hazards model and log rank test stratified by asthma status, prior surgery history, and regions, by considering the first SCS rescue use or surgery (actual or planned) for NP as the event. The entire treatment period in Arms A and the treatment period of 300 mg q2w in Arm B (that is, the first 24 weeks) will be pooled and used as the treatment period by dupilumab 300 mg q2w, and the entire treatment period in Arm C will be used as the treatment period by placebo. For this analysis of proportion of

patients with SCS rescue or surgery (actual or planned) for NP for dupilumab 300 mg q2w and placebo, patients in Arm B will be considered as censored at the end of 300mg q2w treatment. Descriptive statistics including number of patients with rescue or surgery and number of patients without rescue or surgery (censored) and the corresponding rates will be provided by treatment group. The estimates of the hazard ratio and corresponding 95% CI will be provided for dupilumab 300 mg q2w versus the placebo.

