#### *11.4.2.4.2 Analyses of efficacy endpoints for Arm A and Arm B versus placebo at Week 52*

The change from baseline in TSS, SNOT-22, UPSIT, daily loss of smell and LMK at Week 52 will be assessed separately for dupilumab 300 mg q2w (Arm A) and dupilumab 300 mg q2w/q4w (Arm B) versus placebo and will be analyzed using the hybrid method of the WOCF and the MI in the same fashion as for the key secondary endpoints of change from baseline in NC and in NPS at Week 52.

Proportion of patients with first SCS rescue or surgery (actual or planned) for NP during the treatment period up to Week 52 will be assessed separately for dupilumab 300 mg q2w (Arm A) and dupilumab 300 mg q2w/q4w (Arm B) versus placebo and will be analyzed using the same approach as those for the key secondary endpoint of the proportion of patients with SCS rescue or surgery (actual or planned) for NP during the treatment period for dupilumab 300 mg q2w versus placebo. With this approach, proportion of patients with first SCS rescue or surgery (actual or planned) during the treatment period will be derived and analyzed using the Cox proportional hazards model and log rank test stratified by asthma status, prior surgery history, and regions, by considering the first SCS rescue use or surgery (actual or planned) for NP as the event. The entire treatment period in Arms A, B, and C will be used in the analysis, and comparisons will be made between Arms A and C, and between Arms B and C, separately. Descriptive statistics including number of patients with rescue or surgery and number of patients without rescue or surgery (censored) and the corresponding rates will be provided by treatment group. The estimates of the hazard ratio and corresponding 95% CI will be provided for Arms A versus C and Arms B versus C, respectively.

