2.2 DISPOSITION OF PATIENTS

This section describes patient disposition for both patient study status and the patient analysis populations.

Screened patients are defined as any patients who signed the informed consent.

Randomized patients consist of all patients with a signed informed consent form who have had a treatment kit number allocated and recorded in the IRT database, regardless of whether the treatment kit was used.

For patient study status, the total number of patients in each of the following categories will be presented in the clinical study report using a flowchart diagram or summary table:

- Screened patients
- Screen failure patients and reasons for screen failure
- Nonrandomized but treated patients
- Randomized patients
- Randomized but not treated patients
- Randomized and treated patients
- Patients who did not complete the 24-week treatment as per protocol
- Patients who did not complete the 52-week treatment as per protocol
- Patients who discontinued study treatment prior to Week 24 by main reason for permanent treatment discontinuation

- Patients who discontinued study treatment prior to Week 52 by main reason for permanent treatment discontinuation
- Patients who withdraw from study
- Patients who withdraw from study prior to Week 24
- Patients who withdraw from study prior to Week 24 by main reason for study discontinuation.
- Patients who withdraw from study prior to Week 52
- Patients who withdraw from study prior to Week 52 by main reason for study discontinuation.
- Patients who withdraw from study by main reason for study discontinuation
- Vital status at last study contact

For all categories of patients (except for the screened and nonrandomized categories) percentages will be calculated using the number of randomized patients as the denominator. Whether patients received rescue treatment (SCS or NP surgery) by Week 24 and Week 52 will be provided in tables. The tables will list patient numbers and percentages by treatment group and type of rescue treatment (SCS or NP surgery).

All critical or major deviations potentially impacting efficacy analyses, randomization, and drug-dispensing irregularities, and other major or critical deviations will be summarized in tables giving numbers and percentages of deviations by treatment group.

Additionally, efficacy populations will be summarized by number of patients on the randomized population.

- Efficacy population: intent-to-treat (ITT) population

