2.4.4.5 Analyses of exploratory efficacy endpoints

2.4.4.5.1 Analyses of efficacy endpoints for Arm B versus placebo at Week 52

The change from baseline in LMK, TSS, UPSIT, daily assessed loss of smell, VAS for overall rhinosinusitis, EQ-5D utility and daily assessed severity of rhinorrhea at Week 52 and percent change from baseline in NC, TSS, daily assessed loss of smell and VAS for overall rhinosinusitis at Week 52 will be assessed separately for dupilumab 300 mg q2w/q4w (Arm B) versus placebo and will be analyzed using the hybrid method of the WOCF and the MI in the same fashion as for the key secondary endpoints of change from baseline in NC, in NPS and SNOT-22 at Week 52. Descriptive statistics including number of patients, mean, standard error, and least squares (LS) means will be provided. In addition, difference in LS means and the corresponding 95% confidence intervals (CI) will be provided along with the p-values.

For responder type endpoints including

- The proportion of patients with improvement by at least 1 point in NPS and 0.5 reductions in NC at Week 52

The Cochran-Mantel-Haenszel test will be performed on the association between the responder status and treatment group, stratified by asthma/NERD status, prior surgery history, and region. Comparisons of the proportions of responders between dupilumab 300mg q2w/q4w (Arm B) and

placebo will be derived. And corresponding odds ratios and 95% CI will be reported. Patients who are indicated for surgery for NP or receive SCS for any reason will be considered as non-responders for time points after using SCS or surgery. For patients who discontinue treatment without using SCS or surgery, data collected during the off-treatment period will be used to determine the responder/non-responder status. Missing data at Week 52 will be considered as non-responders.

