2.4.4.5.2 Other exploratory analyses

Total SCS dose prescribed (in mg) during the study period and total SCS intake in days and courses during the study period will be summarized by treatment groups. A course of SCS is considered continuous if treatment is separated by less than 7 days. Various doses of systemic corticosteroids will be converted to prednisone-equivalent oral corticosteroid. For patients who discontinue treatment, data collected during the off-treatment period will also be used. Descriptive statistics including number of subjects, mean, standard deviation, min, and max will be provided, and no statistical testing will be conducted.

Proportion and time-to-event of patients requiring rescue treatment with SCS for any reason, SCS for nasal polyps, SCS for respiratory disease, and surgery (planned or actual) for NP will also be performed using the same method as those for the secondary endpoint of the proportion of patients requiring rescue with SCS or NP surgery (actual or planned) during the treatment period for dupilumab 300 mg q2w versus placebo using the pooled data of the two NP studies SINUS-52 (EFC14280) and SINUS-24 (EFC14146).

Change from baseline in decreased/loss of sense of taste symptom severity and SNOT-22 items: "decreased sense of smell/taste", "difficulty falling asleep", "wake up at night", "lack of a good night's sleep", "wake up tired", "fatigue", and "reduced productivity", (FEV1, FVC and FEF25-75 in patients with asthma) at Week 24 and Week 52 will be assessed separately. For analyses at Week 24, dupilumab 300 mg q2w (Arm A and first 24 weeks of Arm B) versus placebo will be analyzed using the hybrid method of the WOCF and the MI in the same fashion as for the primary analysis for co-primary endpoints at Week 24. For analyses at Week 52, dupilumab 300 mg q2w (Arm A) and dupilumab 300 mg q2w/q4w (Arm B) versus placebo and will be analyzed using the hybrid method of the WOCF and the MI in the same fashion as for the key secondary endpoints of change from baseline in NC, in NPS and in SNOT-22 at Week 52. Descriptive statistics including number of patients, mean, standard error, and least squares (LS) means will be provided. In addition, difference in LS means and the corresponding 95% confidence intervals (CI) will be provided.

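### The SAP omits, without declaring it, the protocol's 52-week rescue comparisons of Arm A and Arm B with placebo, so no rescue hazard ratio covers Arm B's q4w phase

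*SAP*

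**What the plan says.** The protocol plans two different rescue analyses.

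- The key secondary analysis (Protocol 11.4.2.2.2) contrasts q2w with placebo. For that purpose "patients in Arm B will be considered as censored at the end of 300mg q2w treatment".
- A separate analysis among the other secondary endpoints (Protocol 11.4.2.4.2, repeated in the synopsis) runs to Week 52. Here "The entire treatment period in Arms A, B, and C will be used in the analysis". Each dupilumab arm is set against placebo on its own, by a Cox model and a log-rank test stratified by asthma status, prior surgery and region. Hazard ratios with 95% intervals "will be provided for Arms A versus C and Arms B versus C, respectively".

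The SAP carries only the first analysis forward. Section 2.4.4.2.3 is headed, and its hazard ratio defined, for q2w versus placebo. Its pooled version with EFC14146 counts, from Arm B, "the treatment period of 300 mg q2w in Arm B (that is, the first 24 weeks) of EFC14280".

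SAP 1.2.3 still lists an Arm B versus Arm C efficacy objective up to Week 52, now as exploratory. SAP 1.5 states that the protocol's statistical section is unchanged, and 1.6 is marked not applicable.

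**The concern.** Arm B exists to show what happens when dosing becomes less frequent after Week 24. A need for steroids or surgery is one of the clearest ways in which loss of control would show. Protocol 4.2 says the study will assess that need over the randomized period and inform on the step-down regimen. The analysis that joins the two aims, Arm B versus placebo for rescue over the full 52 weeks, is in the protocol and missing from the SAP.

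Other Arm B versus C results at Week 52 are kept, with intervals and p-values: NPS, NC and SNOT-22 in SAP 2.4.4.2.2, and LMK, TSS, UPSIT and others in 2.4.4.5.1. Moving Arm B to an exploratory objective therefore does not by itself explain why rescue was left out. A reader who relies on SAP 1.5 would not know that a planned randomized comparison had gone.

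**Working it through.** **1. Where the analysis could sit in the SAP**

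| SAP section | Rescue content |
|---|---|
| 2.4.4.2.3 rescue model | q2w versus placebo only |
| 2.4.4.3 hierarchy | pooled two-study q2w contrast only |
| 2.4.4.4.1 other secondary list | none |
| 2.4.4.4.3 Arm A versus placebo, Week 52 | none |
| Time-course profiles over 24 and 52 weeks | scores and responders only |
| 2.4.4.5.1 Arm B versus placebo, Week 52 | none; scores plus one responder endpoint, "The proportion of patients with improvement by at least 1 point in NPS and 0.5 reductions in NC at Week 52" |
| 2.4.4.5.2 rescue components | q2w versus placebo, pooled studies |

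Two descriptive outputs remain for Arm B after Week 24. In SAP 2.2, "Whether patients received rescue treatment (SCS or NP surgery) by Week 24 and Week 52 will be provided in tables", as numbers and percentages by treatment group. In SAP 2.4.4.5.2, SCS dose, days and courses are summarised by group without testing.

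**2. The protocol's own power figure.** Inputs (Protocol 11.1): 15% rescue on placebo, 5% on dupilumab, 120 versus 240 patients, two-sided alpha 0.05, stated power 87% at a hazard ratio of 0.316.

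- Hazard ratio: ln(0.95)/ln(0.85) = 0.316. It agrees.
- Two proportions: power = Φ[(Δ − 1.96·SE0)/SE1]. Pooled rate = (18 + 12)/360 = 0.0833; SE0 = √[0.0833 × 0.9167 × (1/120 + 1/240)] = 0.0309; SE1 = √[0.15 × 0.85/120 + 0.05 × 0.95/240] = 0.0355. Power = Φ[(0.10 − 0.0606)/0.0355] = Φ(1.11) = 86.7%.
- A simulated log-rank test with all patients followed for 52 weeks gives 88.0%.

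The 87% reproduces, with no dropout and both dupilumab arms followed for 52 weeks.

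**3. What the q2w contrast leaves out.** 52 − 24 = 28 weeks, and 28/52 = 54% of Arm B's planned follow-up. This is the whole q4w phase. With a constant hazard and 5% rescue over 52 weeks, Arm B has 120 × (1 − 0.95^(24/52)) = 2.8 events by Week 24. The other 6 − 2.8 = 3.2 fall in the q4w phase. If the effect were lost entirely at Week 24, about 117 event-free patients would yield 117 × (1 − 0.85^(28/52)) ≈ 10 events there. None of these events would enter a rescue hazard ratio.

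**4. What a restored Arm B versus C analysis could show.** Inputs: 120 versus 120, 15% on placebo. The documents give no rescue rate for q2w/q4w, so the Arm B rate is an assumption. The Schoenfeld formula is Φ(|ln HR|·√(events/4) − 1.96).

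| Assumed Arm B rate | HR | Events | Two proportions | Simulated log-rank | Schoenfeld |
|---|---|---|---|---|---|
| 5% | 0.316 | 24 | 74% | 75% | 81% |
| 7.5% | 0.480 | 27 | 45% | 45% | 48% |
| 10% | 0.648 | 30 | 21% | 22% | 22% |

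For example, at 5%: 1.153 × √(24/4) − 1.96 = 0.86, and Φ(0.86) = 81%. Power is moderate if protection is fully kept and low if it is partly lost.

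**The case against.** The strongest case on the other side has five parts.

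- *The Week 24 cut-off is legitimate.* A reader might infer that the SAP wrongly censors Arm B. The documents do not support that: the protocol sets the rule for this contrast, and it is coherent for a q2w estimate. The SAP's sentence on the first 24 weeks governs the pooled analysis. Its single-study paragraph does not say how Arm B is handled, although the heading limits it to q2w versus placebo. This part stands in full.
- *Arm B rescue is not invisible.* Besides the two descriptive outputs, Week 52 scores for Arm B versus C replace values after SCS or surgery by the worst earlier post-baseline value, and responder analyses count rescued patients as non-responders. More rescue under q4w would worsen those results. This stands, but these analyses mix rescue with symptom change and give no rescue hazard ratio.
- *Events are few.* The SAP itself cites potentially low event numbers in each single study. The power table bears this out, and it argues for an estimate with an interval. Pooling cannot fill the gap, because the arms taken from EFC14146 are q2w and placebo.
- *Arm A is largely covered.* Its whole treatment period is in the pooled Cox model, with Kaplan-Meier estimates to Week 52. This stands, so the A versus C half matters less.
- *Arm B versus C is exploratory and outside the hierarchy.* True. That lowers the weight of the point but does not explain an undeclared omission.

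**Conclusion.** The point holds as an undeclared omission of a planned analysis. Protocol 11.4.2.4.2 has no counterpart in the SAP, SAP 1.5 says nothing changed, and the q4w phase, 28 of Arm B's 52 weeks, contributes to no rescue hazard ratio. It should be put right. It does not touch the co-primary endpoints or the testing hierarchy.

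Two stronger readings go too far. One is that rescue under step-down goes unreported; the tables and the SCS summaries contradict that. The other is that the missing comparison would be a well-powered test. The 81% figure comes from the most favourable formula and assumes that Arm B keeps the full 5% rate. The other two methods give 74–75% at that rate, and all three give 21–22% at 10%.

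The event counts and power figures assume constant hazards, no dropout and the protocol's rates. Those rates refer to SCS for nasal polyps or planned surgery. The SAP endpoint (2.1.3.2.1.6) covers SCS for any reason, so actual counts may be higher.

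**What to change.** Restore the protocol's analysis in SAP 2.4.4.4.3 (Arm A versus C) and 2.4.4.5.1 (Arm B versus C):

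- time to first SCS use or nasal polyp surgery (actual or planned) over the full 52 weeks, with a Cox hazard ratio and 95% interval, the stratified log-rank test, and Kaplan-Meier probabilities for each arm;
- a statement of whether the event is SCS for nasal polyps, as in the protocol, or SCS for any reason, as in the SAP;
- placement outside the hierarchy, presented as estimation.

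Record any remaining departure from the protocol, with its reason, in SAP 1.5. If the sponsor prefers not to restore the analysis, its removal should be declared and justified there.

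A comparison that starts at Week 24 may look like a natural supplement. It is not in the protocol, and it conditions on patients still event-free after randomization. Leave it out or label it descriptive.

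The cost is SAP wording, two tables and one figure, with no new data. The downside is a few more unadjusted exploratory p-values.
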